Blood-based glutathione cycle biomarkers		✓	✓	✓		✓	✓		✓
Urine-based biomarkers		✓	✓	✓		✓	✓		✓
Lumbar puncture (CNS)			✓			✓			
ALSFRS-R		✓	✓	✓		✓	✓		✓
Water and solid swallowing tests			✓			✓			✓
Speech assessment			✓			✓			✓
Handheld dynamometry			✓			✓			✓
AE/SAE Assessment			✓	✓	√e	✓	✓	√e	√ g
Drug plasma concentration ^f				√f		√f			
Concomitant medications	✓		✓	✓	√e	✓	✓	√e	√ g
Dosing Schedule				Month 1	Month 2	Month 3			
EPI-589 BID				✓	✓	✓			

- a. Height measurement need not be repeated after treatment begins.
- b. Physical examination includes breast examination in women at screening.
- c. Urine or Serum pregnancy test will be done for of child bearing potential only.
- d. Run-in assessments must be performed 30 Days (+/- 3 days) prior to baseline after confirmation of eligibility and enrollment in the study.
- e. Month 2 assessments and Withdrawal Phase Month 5 assessments can be conducted by telephone.
- f. Samples will be collected at 0-hour and 0.5, 1, 2, 4, 6, 8, and 12 hours post-dose on study visit days. 12 hour PK can be obtained at time 0.
- g. AEs reported at Month 6 (and any associated concomitant medications) must be followed for 30 days; this follow-up may be conducted by telephone
- h. Screening values can be used if done within one month of baseline and if completed under fasted conditions

Version: Amendment 2.0

III. BACKGROUND INFORMATION AND RATIONALE

A. Overview of Amyotrophic Lateral Sclerosis (ALS)

Amyotrophic lateral sclerosis (ALS) is a fatal neurodegenerative disease without an effective therapy. ALS causes progressive damage and loss of motor neurons in the central and peripheral nervous systems that result in a gradual decrease and loss of motor and brainstem function. ALS is estimated to occur in 1–2/100,000 people worldwide. The majority of ALS cases are sporadic, however about 10% of cases are inherited (familial ALS), with 20% of familial ALS resulting from mutant forms of the superoxide dismutase soluble gene (SOD1), a homodimer that converts superoxide radicals to molecular oxygen in mitochondrial membranes and cytoplasm. Symptoms of motor neuron death in sporadic and familial ALS are clinically indistinguishable. The role of oxidative stress (OS) and mitochondrial dysfunction as key pathophysiological features in all forms of ALS has been well established.¹

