The primary objective is to evaluate the effects of EPI-589 on safety as assessed by occurrence of drug-related serious adverse events in subjects with ALS.

B. Secondary Objectives

The secondary objectives are to evaluate the effects of EPI-589 in subjects with ALS on:

- 1. Glutathione cycle biomarkers as measured in blood, cerebral spinal fluid, and urine
- 2. Disease progression as assessed by ALS Functional Rating Scale-Revised
- 3. Respiratory function as assessed by pulmonary function tests and capnography
- 4. Failure to thrive as measured by body weight
- 5. Swallowing as assessed by change in water and solid swallowing tests
- 6. Speech as assessed by speech evaluation
- 7. Muscle function as assessed by handheld dynamometry
- 8. Drug plasma concentration measurements
- 9. Hematology, blood chemistry, electrocardiogram

V. INVESTIGATIONAL PLAN

A. General Schema of Study Design

After study enrollment, baseline assessments will be performed. Subjects participate in a 30-day run-in phase to establish baseline ALS disease-related clinical and biomarker features. EPI-589 will then be administered for 3 months, unless discontinued for safety or tolerability issues. All subjects will then be followed for an additional 90 days to determine long-term effects, duration of response to treatment, and potential effects of EPI-589 therapy on known disease trajectory.

A1. Screening Phase

Suitable candidates for the trial will receive a short overview of the study by the Investigator's staff and, if interested, will undergo Screening. The Investigator will inform each prospective subject of the nature and details of the study, explain the potential risks and must obtain written informed consent from the subject or their legally authorized representative prior to performing any study related procedures.

A2. 30-Day Run-in Phase

Once eligibility is confirmed, the subject will be enrolled in the study and the ALS Functional Rating Scale-Revised (ALSFRS-R) measurements and CNS, urine-based and blood-based glutathione cycle biomarkers, will be collected.

A3. Baseline

ALSFRS-R, lumbar puncture, swallowing, speech, handheld dynamometry, blood-based biomarkers, urine biomarkers, and clinical measurements will be collected.

A4. Treatment Phase

EPI-589 dosing will start on Day 1. Subjects will self-administer EPI-589 at a dose of 500 mg BID.

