D2. Exclusion Criteria

- 1. Allergy to EPI-589
- 2. Use of invasive or non-invasive ventilation
- 3. Participation in other intervention studies
- 4. Diagnosis of any other neurologic disease
- 5. Malignancy within past two years
- 6. Pregnant or plans to become pregnant
- 7. History of stroke
- 8. History of brain surgery
- 9. Hepatic insufficiency with liver function tests (LFTs) greater than three times upper limit of normal (ULN)
- 10. Renal insufficiency requiring dialysis
- 11. End stage cardiac failure
- 12. Participation in a trial of a device, drug or other therapy for ALS within 3 months of screening and for the duration of the trial.

VI. STUDY PROCEDURES

A. Screening (-30 days \pm 3 days) Visit

A1. Screening

The Investigator will inform each prospective subject of the nature of the study, explain the potential risks, and obtain written informed consent from the subject prior to performing any study-related procedures and prior to the administration of study drug. Screening evaluations consist of the following:

- 1. Assessment of eligibility
- 2. Medical history, chart review
- 3. Physical examination (including breast examination for women)
- 4. Height, weight and vital signs
- 5. Receipt and review of all previous testing
- 6. 12-lead ECG
- 7. Pulmonary function assessment
- 8. Hematology including coagulation, serum chemistry, urine analysis
- 9. Pregnancy test (women of childbearing potential must have a negative serum or urine pregnancy test)
- 10. Concomitant medication assessment (last 60 days prior to enrollment)

A2. Run-in Assessments

Run-in assessments must be performed 30 days (+/- 3 days) prior to baseline after eligibility is confirmed and subject is enrolled in the study. Run-in evaluations consist of the following:

- 1. ALS Functional Rating Scale-Revised
- 2. Blood-based glutathione cycle biomarkers
- 3. Urine-based glutathione cycle biomarkers

B. Treatment Phase

If the subject is eligible for the study following all screening procedures and is still willing to participate in the study, the subject must return to the clinic 30 days (+/- 3 days) for baseline assessments. In-clinic study visits are scheduled at Month 1 and Month 3. Month 2 assessments can be conducted via telephone. End of treatment will be at the Month 3 study visit. Pharmacokinetic sampling takes place at Month 1 and Month 3.

B1. Baseline Assessments

The following will be assessed or performed at this visit:

- 1. Physical examination

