- 2. 12-Lead ECG
- 3. Pulmonary function assessment and capnography
- 4. Hematology including coagulation and serum chemistry*
- 5. Weight and vital signs
- 6. Pregnancy test (women of childbearing potential)
- 7. Glutathione cycle blood, urine and CNS biomarkers
- 8. C-SSRS
- 9. ALS Functional Rating Scale-Revised
- 10. Water and solid swallowing tests
- 11. Speech assessment
- 12. Handheld dynamometry

EPI-589 will be dispensed to the subjects along with the dosing diary. Subjects will self-administer EPI-589 at a dose of 500 mg BID starting from Day 1.

* Screening values can be used if done within one month of baseline and if completed under fasted conditions

B2. Study Visit Assessments

Adverse events and concomitant medication information will be reviewed and assessed at each visit.

Clinic Visits: Month 1 and Month 3

The following will be assessed or performed at the Month 1 (Day 29 +/-3 days) clinic visit:

- 1. Physical examination
- 2. 12-lead ECG
- 3. Pulmonary function assessment and capnography
- 4. Hematology including coagulation and serum chemistry
- 5. Weight and vital signs
- 6. Pregnancy test (women of childbearing potential)
- 7. Glutathione cycle blood, urine, and CNS biomarkers
- 8. ALS Functional Rating Scale-Revised
- 9. Drug plasma concentration measurements*

The following will be performed at the Month 3 (Day 85 +/- 3 days) clinic visit:

- 1. Physical examination
- 2. 12-lead ECG
- 3. Pulmonary function assessment and capnography
- 4. Hematology including coagulation and serum chemistry
- 5. Weight and vital signs
- 6. Pregnancy test (women of childbearing potential)
- 7. Glutathione cycle blood, urine, and CNS biomarkers
- 8. Drug plasma concentration measurements*
- 9. ALS Functional Rating Scale-Revised
- 10. Water and solid swallowing tests
- 11. Speech assessment
- 12. Handheld dynamometry

Drug accountability and compliance: Subjects should bring the study medication and the dosing diary at the Month 1 and Month 3 visits. All the used and unused study medication should be returned and reconciled at the Month 3 visit.

Month 2 Assessments

Month 2 assessments can be conducted by telephone and will include review of concomitant medications and AEs.

B3. Early Termination of Study Medication

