- 4. General: creatine phosphokinase (CPK), CK fractionated (CK-MB, CK-MM and CK-BB) and troponin (baseline only), protein (total), albumin, calcium, magnesium, glucose, phosphate
- 5. Lipids: cholesterol (total), high-density lipoprotein (HDL) cholesterol, low-density lipoprotein (LDL) cholesterol, cholesterol/HDL Ratio (calculated), non-HDL cholesterol (calculated) and triglycerides

f. Pregnancy Test

Serum or urine human chorionic gonadotropin (HCG), beta subunit, will be performed on all subjects of childbearing potential at each study visit through to the end of treatment.

Diagnoses associated with any NIH Common Toxicity Criteria (CTC) v4.03 Grade 3 or 4 laboratory abnormalities will be recorded as AEs on the CRF. Repeated and verified laboratory tests that meet at least Grade 3 AE requirements will be reported to the institutional review board (IRB) per institutional requirements. The recorded AEs should indicate the underlying abnormality or diagnosis (e.g., renal insufficiency) if known, as opposed to the observed deviation in laboratory results (e.g., elevated creatinine). Any additional relevant laboratory results obtained by the Investigator during the study will be supplied to the Sponsor.

Laboratory tests that result in significantly abnormal values should be repeated for verification. Additional tests and other evaluations required to establish the significance or etiology of an abnormal result, or to monitor the course of an AE, should be obtained when clinically indicated. In particular, if a clinically significant abnormal result is observed that is not resolved by the final study visit, repeat tests should be performed to document resolution or stability of the abnormality.

D. Sample Collection Procedures, Bioanalytical Methods and Sample Shipment

Urine, cerebral spinal fluid, and fasting blood samples will be collected for determination of levels of glutathione cycle markers. Additional information about the collection, handling, storage, and shipment of the glutathione cycle marker samples will be provided separately prior to start of the study.

E. Efficacy Evaluations

E1. Glutathione

Blood, urine, and cerebral spinal fluid levels of oxidized glutathione (GSSH) and reduced glutathione (GSH) as well as glutathione metabolites will be used to evaluate EPI-589 target engagement and ability to correct key biochemical aspects of disease pathology.

E2. ALS Functional Rating Scale-Revised (ALSFRS-R)

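### Fasted screening safety laboratory values up to a month old may replace the Day 0 draw, so the first on-treatment comparison can span 53 to 63 days, about half of them untreated

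*Protocol*

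**What the plan says.** The schedule in Protocol section II marks serum chemistry and hematology (including the coagulation panel) at Screening, Day 0, Month 1 and Month 3. The two Day 0 cells carry footnote h: "Screening values can be used if done within one month of baseline and if completed under fasted conditions". Section VI.B1 (Baseline Assessments) repeats the sentence as an asterisk on the same laboratory item.

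The timing rules around it are these:

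- Screening is at Day -30 ± 3 (sections II and VI.A).
- Run-in assessments are also at 30 ± 3 days before baseline, and come after eligibility is settled (section II, footnote d; VI.A2). Section V.A2 puts it as: "Once eligibility is confirmed, the subject will be enrolled in the study".
- At the baseline visit, "EPI-589 will be dispensed to the subjects along with the dosing diary" (VI.B1). Dosing starts on Day 1 (V.A4).
- The next scheduled safety laboratory tests are at the "Month 1 (Day 29 +/-3 days) clinic visit" (VI.B2), then at Month 3 (Day 85 ± 3). None are scheduled in the withdrawal phase.

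Section IV.B lists "Hematology, blood chemistry, electrocardiogram" as secondary objective 9, and section VIII.C includes clinical laboratory data in the safety analysis.

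**The concern.** The study has one arm and describes itself as subject-controlled, so a laboratory change has to be read against the same subject's pre-dose value. If that value is about a month old, a difference first seen at Month 1 mixes about a month without drug and about a month on it. The error can go either way: a rise during run-in can pass for a drug effect, and a fall during run-in can mask one.

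The waiver also removes a useful internal comparison. With a Day 0 draw, each subject has two pre-dose values about 30 days apart, which shows how much the tests move untreated over roughly the length of the first treatment interval. Under the waiver a subject may have only three scheduled laboratory points, one of them pre-dose. Because the option is discretionary, the cohort may mix intervals of about four and about eight weeks.

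A current pre-dose value has some relevance for this drug. Section III.D1 reports hematology changes consistent with hemolysis in rats and AST/ALT elevations in monkeys at the high dose. Section X.D2 relies on laboratory tests to reveal drug effects before they become clinically important.

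**Working it through.** The protocol states no figure for this interval, so there is none to reproduce. The check is interval arithmetic on the visit windows.

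**Inputs**

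- Screening draw: 27 to 33 days before Day 0 (sections II, VI.A).
- Reuse limit: one month. The protocol does not define a month in days, so 28, 30 and 31 days are all tried.
- First dose: Day 1 (V.A4).
- Month 1: Day 29 ± 3, that is Day 26 to 32 (VI.B2).

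**Age of a reused value at Day 0** = overlap of 27 to 33 days with the one-month limit.

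- 31-day month: 27 to 31 days.
- 30-day month: 27 to 30 days.
- 28-day month: 27 to 28 days.

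Draws at Day -32 and Day -33 are inside the screening window but never qualify. The nominal Day -30 qualifies under a 30- or 31-day month.

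**Interval from the reused value to Month 1** = age at Day 0 + Month 1 day.

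- Shortest: 27 + 26 = 53 days.
- Longest: 31 + 32 = 63 days (30 + 32 = 62 with a 30-day month; 28 + 32 = 60 with a 28-day month).
- Nominal: 30 + 29 = 59 days.
- With a Day 0 draw: 26 to 32 days, nominal 29.

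**Untreated share** = (age at Day 0 + 1) / interval, counting up to first dose on Day 1.

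- Lowest: sample on Day -27, Month 1 on Day 32: 28/59 = 47%.
- Highest: sample on Day -31, Month 1 on Day 26: 32/57 = 56% (31/56 = 55% with a 30-day month).
- Nominal: 31/59 = 53%. With a Day 0 draw only 1 of 29 days is untreated.
- Counting to Day 0 instead: 27/59 = 46% to 31/57 = 54%, nominal 30/59 = 51%.

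**Effect of laboratory turnaround.** Run-in must follow confirmed eligibility, and the liver-test exclusion needs a result. Run-in can be no later than Day -27, so a Day -27 screening draw needs a same-day result. If turnaround is taken as 2 days (an assumption), the latest usable draw is Day -29. Reusable values are then 29 to 31 days old (29 to 30 with a 30-day month), and the interval starts at 29 + 26 = 55 days. The upper end does not move. Under a 28-day month with that turnaround, no draw would qualify.

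**Month 3 comparison.** With Month 3 at Day 82 to 88, the interval is 27 + 82 = 109 to 31 + 88 = 119 days, instead of 82 to 88. About a quarter is untreated (27/115 = 23% to 31/113 = 27%, counted to Day 0).

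**The case against.** The strongest reply is that nothing here is contradictory. The footnote and the asterisk agree, the rule is optional, bounded in time and limited to fasted samples, and the Day 0 draw remains the default. The protocol sets no change-from-baseline formula for safety laboratory tests and plans no formal comparisons, and the definition of a laboratory baseline normally belongs to the SAP. That is fair as far as it goes: the first laboratory change is an inference from the schedule. But an SAP can only choose among samples that exist; it cannot recover one that was never drawn.

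The reach may be small, and this stands. Unfasted samples do not qualify, many screening draws may fall too early, and uptake is unknown. Stable riluzole and supplements for 30 days before enrollment may also make run-in shifts uncommon, and section III.D2 reports no clinically relevant laboratory change in the multiple-dose study in healthy subjects.

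Other safeguards exist: examination, vital signs and ECG at Day 0, additional tests when clinically indicated, and repeat testing of significantly abnormal values. They help, but none supplies a routine pre-dose laboratory value.

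The blood limit of under 100 mL (VII.C1.c) could be strained. The schedule implies 14 to 16 pharmacokinetic samples, 6 glutathione samples and 3 safety panels under the waiver: 23 to 25 collections, or about 4 mL each (100/25 = 4.0; 100/23 = 4.3). Tube volumes are not given, so this cannot be settled. As the Day 0 panel is the schedule's default, however, the limit should already allow for it.

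Two stronger readings are tempting, and the document supports neither:

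- A reader might infer that the waiver removes a pre-dose check of the liver-test exclusion. It does not. Eligibility is checked at screening, and return for baseline is conditioned on it: "If the subject is eligible for the study following all screening procedures and is still willing to participate in the study". Drug is dispensed at the baseline visit without waiting for Day 0 results, so even with a Day 0 draw the protocol does not make dosing depend on the result.
- A reader might infer that the waiver leaves the troponin measurement unclear. Section VII.C1.e limits troponin to baseline, so there is no screening value to reuse and the waiver does not reach it.

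**Conclusion.** The point holds as a minor design weakness. When the option is used, the only scheduled pre-dose chemistry, hematology and coagulation values are about 27 to 31 days old at Day 0, and the Month 1 comparison covers about 53 to 63 days (59 nominal) instead of 26 to 32. Roughly half of that interval is untreated. Attribution of laboratory changes is weaker, and a run-in change may not be seen until Month 1, after about four weeks of dosing.

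The range rests on two readings. The 31-day and 63-day ends need a 31-day month, and the 27-day and 53-day ends need a same-day eligibility result. Neither affects the conclusion that about half the interval is untreated.

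The consequence is limited to the secondary safety laboratory data. The primary endpoint, drug-related serious adverse events, is not directly altered. The glutathione markers and ALSFRS-R carry no such waiver and keep their own Day 0 measurements. The number of subjects affected, and how often laboratory values shift during run-in, cannot be derived from the protocol.

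**What to change.** Delete footnote h in section II and the asterisk with its note in VI.B1, so that chemistry, hematology and coagulation are always drawn at Day 0 alongside the fasting glutathione blood. Add to VI.B1 that the Day 0 results are reviewed as soon as they are available. The Month 1 comparison then covers 26 to 32 days, nearly all on treatment, and every subject has two pre-dose values.

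The cost is at most one set of laboratory tubes per subject, about 20 sets in all, counted within the existing limit of under 100 mL. The visit and a fasting blood draw are already scheduled that day, so no visit is added. The sponsor should confirm the total against actual tube volumes, which the protocol does not give.

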Open label with 30-day run-in phase to establish baseline parameters and a 90-day withdrawal phase to determine duration of treatment response.

Study duration

Run-in phase: 1 month Treatment phase: 3 months Withdrawal phase: 3 months

Planned number of

subjects

Approximately 20 subjects

Protocol EPI589-15-001 Version: Amendment 2.0

Test product, mode of administration, strength, and dose

Test Product

EPI-589 in a tablet formulation at a strength of 250 mg

Mode of Administration

Oral with food

Dose

EPI-589 500 mg BID

Reference therapy (for controlled studies)

None

Safety monitoring

Clinical

- 1. Physical exam and vital signs
- 2. Evaluation of adverse events
- 3. 12-lead Electrocardiogram
- 4. Columbia Suicide Severity Rating Scale (C-SSRS)

Laboratory

- 1. Routine serum chemistries
- 2. Routine hematology tests and coagulation tests

Inclusion Criteria

- 1. Diagnosis of possible, probable, laboratory supported probable or definite amyotrophic lateral sclerosis (ALS) by El Escorial Criteria
- 2. or between 21 and 70 years of age
- 3. Forced vital capacity (FVC) \geq 70% of predicted
- 4. Onset of weakness within 3 years as documented in clinical records
- 5. Agreement to use contraception if within reproductive years
- 6. Willingness and ability to comply with study procedures
- 7. Stable regimen of dietary supplements for 30 days prior to enrollment
- 8. Abstention from use of other investigative or non-approved drugs
- 9. Subjects on riluzole must be on a stable dose for at least 30 days prior to study enrollment.
- 10. Subject must be able to swallow 0.375 x 0.700 inch tablets.

Exclusion Criteria

- 1. Allergy to EPI-589
- 2. Use of invasive or non-invasive ventilation
- 3. Participation in other intervention studies
- 4. Diagnosis of any other neurologic disease
- 5. Malignancy within past two years
- 6. Pregnant or plans to become pregnant

- 7. History of stroke
- 8. History of brain surgery
- 9. Hepatic insufficiency with liver function tests (LFTs) greater than three times upper limit of normal (ULN)
- 10. Renal insufficiency requiring dialysis
- 11. End stage cardiac failure
- 12. Participation in a trial of a device, drug or other therapy for ALS within 3 months of screening and for the duration of the trial

Treatment

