In MAD study EPI589-14-001, EPI-589 was rapidly absorbed following oral administration and the median C_{max} was attained within 1 hour (0.50 to 0.76 hours) under fasted conditions after single or multiple dosing among these five cohorts. The mean half-life of EPI-589 ranged from 5.64 to 8.47 hours among these five cohorts. In general, the mean values of the time to peak concentration (T_{max}), half-life ($t_{1/2}$), apparent terminal constant (λz), accumulation ratio (AR), percent fluctuation (%F) and accumulation index (AI) of EPI-589 were similar among the five cohorts.

It appears that no significant effects of age and smoking on EPI-589 pharmacokinetics were observed in this study.

Dose proportionality existed in the exposures (AUC_{0-tau}, C_{max}, C_{min} and C_{avg}) over the dose range of 250 to 500 mg BID EPI-589 under fasted conditions.

F. Clinical Study

EPI589-15-001: A Phase 2A Safety and Biomarker Study of EPI-589 in Subjects with Amyotrophic Lateral Sclerosis.

G. Selection of Drugs and Dosages

The study drug in this trial is EPI-589 (common chemical name (R)-troloxamide quinone).

Each tablet contains 250 mg of EPI-589. The study dose is 500 mg BID, to be maintained in the absence of treatment-emergent toxicity. EPI-589 tablets must be taken with food.

H. Number of Subjects to Enroll in Study

Approximately 20 subjects with ALS.

I. Compliance Statement

This study will be conducted in full accordance with all applicable research policies and procedures, all applicable US federal and local laws and regulations including 45 CFR 46, 21 CFR Parts 50, 54, 56, 312 and 314, and the Good Clinical Practice: Consolidated Guideline approved by the International Conference on Harmonization (ICH). Any episode of noncompliance will be documented.

The investigators will perform the study in accordance with this protocol, obtain consent and report AEs in accordance with local institutional policies and procedures and all EU and US federal requirements. Collection, recording, and reporting of data will be accurate and will ensure the privacy, health, and welfare of research subjects during and after the study.

J. Relevant Literature and Data

Literature references have been provided in Section XV. Additional information can be found in the Investigator's Brochure.

IV. STUDY OBJECTIVES

A. Primary Objective

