Subjects who terminate from the study after receiving first dose and prior to the completion of the treatment phase should have an end of study visit as soon as possible. All the Month 3 visit assessments should be completed at this visit.

C. Withdrawal Phase and Study Completion

Month 4 Clinic Visit (Day 113 +/- 1 Week)

- 1. Physical examination
- 2. Weight and vital signs
- 3. Blood-based biomarkers
- 4. Urine-based biomarkers
- 5. C-SSRS
- 6. ALS Functional Rating Scale-Revised
- 7. AEs and SAEs
- 8. Concomitant medications

^{*}Pharmacokinetics: Plasma concentration samples will be collected at 0-hour and 0.5, 1, 2, 4, 6, 8, and 12 hours post-dose at the Month 1 and Month 3 clinic visits.

Month 5 Assessments

Month 5 assessments may be conducted by telephone.

- 1. AEs and SAEs
- 2. Concomitant medications

Month 6 Clinic Visit (Day 169 +/- 1 Week)

- 1. Physical examination
- 2. Weight and vital signs
- 3. Glutathione cycle blood-based biomarkers
- 4. Glutathione cycle urine-based biomarkers
- 5. ALS Functional Rating Scale-Revised
- 6. Water and solid swallowing tests
- 7. Speech assessment
- 8. Handheld dynamometry
- 9. Pulmonary function tests and capnography
- 10. AEs and SAEs
- 11. Concomitant medications

Subjects who have an ongoing AE at the time of study completion will be followed for up to 30 days, until the event resolves, or until the Sponsor and the Investigator agree that further follow-up is not medically necessary.

D. Unscheduled Visits

If a subject returns to the clinic outside of the normal treatment visit windows, assessments will be made at the Investigator's discretion. All relevant unscheduled visit data will be recorded in the CRF using the supplemental visit CRF pages.

E. Concomitant Medication

Any medication taken by a subject \leq 60 days prior to enrollment and during the course of the study and the reason for use of the medication will be recorded on the case report form (CRF). During screening, each subject will be instructed to report the use of any medication to the Investigator. Subjects will also be instructed about the importance of not taking any medication throughout the study (including over-the-counter [OTC] medications) without first consulting the Investigator.

F. Prohibited Medications

The following are prohibited while the subject is on study treatment:

- 1. Use of antioxidants, specifically vitamins E and C beyond the recommended daily allowance

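### The C-SSRS, a listed safety variable, is never scheduled during treatment, and the early-termination visit reuses a list that omits it

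*Protocol*

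**What the plan says.** The synopsis (Section I) lists the C-SSRS as the fourth clinical item under safety monitoring and again as the fourth clinical item under safety variables.

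The timing is set in these places:

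- **Section II, Schedule of Assessments:** the C-SSRS row has two ticks, Day 0 (Baseline) and Month 4.
- **Section VI.B1:** the C-SSRS is item 8 of the baseline list.
- **Section V.A4:** "EPI-589 dosing will start on Day 1", so the baseline reading comes before any exposure.
- **Section VI.B2:** the Month 1 list has 9 items and the list introduced by "The following will be performed at the Month 3 (Day 85 +/- 3 days) clinic visit" has 12. Neither includes the C-SSRS. The Month 2 contact covers adverse events and concomitant medications only.
- **Section VI.B:** "End of treatment will be at the Month 3 study visit".
- **Section VI.C:** the C-SSRS is item 5 at the Month 4 visit (Day 113, window one week either side). It is not listed at Month 5 or Month 6.
- **Section VI.B3:** the early-termination visit applies to "Subjects who terminate from the study after receiving first dose and prior to the completion of the treatment phase". Its content is set by one sentence: "All the Month 3 visit assessments should be completed at this visit".

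**The concern.** A safety scale is normally read while subjects are exposed. Here the only readings are one before the first dose and one in the Withdrawal Phase. Of the synopsis safety variables that have a row in Section II, the C-SSRS is the only one with no on-treatment tick: AE/SAE review, ECG, serum chemistry and hematology with coagulation are all done at Month 1 and Month 3. The protocol does not explain the difference.

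Two things are at stake:

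- **Early leavers.** They may leave for tolerability or well-being reasons, and a safety scale is then most informative. Their last visit copies a list without the C-SSRS, so baseline is their only scheduled reading.
- **Completers.** With no reading at the end of treatment, a positive finding at Month 4 is hard to assign to the treatment period or to the period after withdrawal.

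Section X.B1 names depression among the events expected as ALS progresses, so findings on this scale are plausible in this population and their timing will matter. This is a gap in data collection, so an analysis plan cannot repair it.

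**Working it through.** The protocol states no figure for the gap, so there is nothing of its own to reproduce. The check is a map of the visits followed by window arithmetic.

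**1. Scheduled C-SSRS readings by visit**

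| Visit | Study day | C-SSRS in Section II | C-SSRS in Section VI list |
|---|---|---|---|
| Baseline | 0 | yes | yes (item 8) |
| Month 1 | 29 ± 3 | no | no (9 items) |
| Month 2 | telephone permitted | no | no |
| Month 3, end of treatment | 85 ± 3 | no | no (12 items) |
| Early termination | after first dose, before the treatment phase is complete | no column | copies the Month 3 list: no |
| Month 4 | 113 ± 7 | yes | yes (item 5) |
| Month 5 | telephone permitted | no | no |
| Month 6 | 169 ± 7 | no | no |

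The table and the lists agree with each other. Readings on treatment: 0 of 2. Scheduled post-baseline readings for a subject who leaves the study during treatment: 0.

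**2. Gap from end of treatment to the only post-baseline reading**

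- Month 3 window: 85 − 3 = Day 82 to 85 + 3 = Day 88.
- Month 4 window: 113 − 7 = Day 106 to 113 + 7 = Day 120.
- Nominal gap: 113 − 85 = 28 days.
- Shortest: 106 − 88 = 18 days.
- Longest: 120 − 82 = 38 days.

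This takes the Month 3 visit as the end of treatment, as Section VI.B states. If three months were instead read as calendar Day 90 to 91, the gap would run from 106 − 91 = 15 to 120 − 90 = 30 days. The conclusion does not change.

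**3. Drug exposure at the Month 4 reading (context only)**

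Section III.E reports: "The mean half-life of EPI-589 ranged from 5.64 to 8.47 hours among these five cohorts". Those cohorts were fasted healthy volunteers. Taking the last dose at the Month 3 visit, half-lives elapsed = days × 24 / half-life in hours:

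- Nominal gap: 28 × 24 / 8.47 = 79 to 28 × 24 / 5.64 = 119.
- Shortest gap with the longest half-life: 18 × 24 / 8.47 = 51.

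Plasma drug is therefore gone by Month 4. That reading can inform on treatment only as far back as the interview's recall reaches.

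**The case against.** Five arguments can be made for leaving the schedule alone.

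- **No passages conflict on timing.** This is true. The schedule and the lists agree, so the point concerns a design choice and not an inconsistency.
- **The C-SSRS has a light role.** It is absent from the objectives, from the secondary safety endpoints in VII.C and from the safety analysis in VIII.C, and it is described under Efficacy Evaluations (VII.E6). No stated endpoint depends on it. This limits the priority, but the synopsis still names it twice as a safety measure.
- **Date of interview is not period covered.** If recall runs back to the previous administration, Month 4 covers the whole treatment period for completers, and current plasma levels matter little. This is the strongest objection and it stands in part: for completers the loss depends on a recall period the protocol does not state. It does not help subjects who leave the study before Month 4.
- **Other safeguards exist.** Adverse events are reviewed at each visit, unscheduled visits allow discretionary assessments (VI.D), and VI.G calls for evaluations of non-completers and follow-up of unknown withdrawal reasons. These narrow the risk, but none requires the C-SSRS.
- **The benefit is small.** In a single-arm study of about 20 subjects, one further reading cannot separate a drug effect from the disease. That is correct. The reading would improve ascertainment and timing, not attribution.

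**Conclusion.** The concern holds. Followed exactly, the protocol collects no C-SSRS during treatment. The only post-baseline reading comes 28 days (18 to 38) after the Month 3 visit, and subjects who leave the study during treatment have no scheduled post-baseline reading.

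The loss is certain for those early leavers. For completers it is conditional on the form's recall period. A subject who stops the drug but stays in the study can still be read at Month 4. The protocol gives no dropout rate, so the number affected cannot be estimated.

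The primary endpoint, drug-related serious adverse events, is not affected. Priority is minor to moderate: worth correcting because the correction is cheap, not because it threatens the trial's main conclusion. The conclusion rests on the visit windows as written and on the Month 3 visit as the end of treatment.

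**What to change.** Bring the C-SSRS schedule into line with its stated safety role:

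1. Add the C-SSRS to the Month 3 list in Section VI.B2.
2. Add a tick in the Month 3 column of the C-SSRS row in Section II.

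Section VI.B3 then carries it to the early-termination visit with no further edit. Post-dose pharmacokinetic samples are taken at Month 3, so the reading there would fall on treatment. It would also separate the treatment period from the withdrawal period when Month 4 is interpreted. Months 1 and 2 would still have no reading of their own.

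One optional editorial change is to move the description in VII.E6 from Efficacy Evaluations to the safety evaluations.

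The cost is one list item, one table cell, a few minutes of questionnaire time and some extra results to review. No new visit, specimen or procedure is needed, and neither dosing nor clinical management changes.
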